6.6. USAGE OF ANALYSIS POPULATIONS

Table 4 : Definitions Use of analysis sets

	ENR	SAF	MITT	PP
Subject disposition	X			
Subject discontinuation	X		X	
Protocol deviations			X	
Subject demographics		X	X	X
Implant characteristics		X	X	X
Valve characteristics		X	X	X
CT Scan		X	X	X
Medical history		X	X	X
Other baseline characteristics		X	X	X
Healthcare Economics		X	X	
Compliance			X	X
Primary endpoint			X	X
Secondary efficacy endpoint		X	X	X
Secondary Cost effectiveness Analysis		X	X	
Analysis of Adverse Events	X	X	X	
Other safety parameter		X	X	

7. DISPOSITION

7.1. SUBJECT DISPOSITION

All presentations for subject disposition will be by treatment group, and overall.

For describing the subject disposition, the following populations will be summarized:

- Subjects enrolled and eligible (overall)
- Subjects eligible but not randomized and reason for non-allocation (overall)
- Subjects randomized
- Subjects implanted, implanted with the planned valve, who crossed the arm, implanted with a non-study device, not implanted
- Subjects in each analysis population
- Subjects on-trial
- Trial completers
- Subjects who discontinued the trial prematurely (and reason).

For the overall report, the percentage denominator will be the number of enrolled subjects. For the “by treatment group” calculations, the percentage denominator will be the number of randomized subjects within each arm.

7.2. SUBJECT DISCONTINUATION

If more than 30% of randomized subjects discontinue the study the distribution of the time to discontinuation from study will be summarized using time-to-event methods (section 5.2). The time from randomization to discontinuation will be censored at the End-of-Study Visit or Analysis cut-off date.

In addition, the following information will be provided descriptively summarized:

- Study length
- Extent of exposure and total patient-years

7.3. PROTOCOL DEVIATIONS

All protocol deviations (PDs) will be summarized overall (ENR) and by arm (ITT) by severity (minor and major) and grouped into different categories:

- Inclusion/Exclusion
- Informed Consent
- Procedure Performed by Unauthorized Physician
- Visit/Follow-up Not Done

- Visit/Follow-up Out of Window
- Assessment/Procedure Incomplete/Not Done
- Assessment/Procedure Out of Window
- Planned Surgical Approach Changed
- Randomization
- Study Device Not Used per IFU or per Protocol
- Serious Adverse Event Not Reported per Protocol
- Other

PDs will be reported as:

- total PDs on the total number of patients
- number of subjects with at least one PD on the total number of patients

Protocol deviations will be presented in a subject data listing.

8. DEMOGRAPHICS AND OTHER BASELINE CHARACTERISTICS

The demographics/baseline characteristics will be analyzed by means of summary statistics (section 5.2) according to the nature of the variable (continue or discrete). Statistical tests for comparison of demographic and baseline characteristics between treatment groups will be performed according to the nature of the variable. A total of around 100 demographic and baseline variables will be compared, therefore a Bonferroni correction will be applied in order to take into account the multiple comparison. Given the correction, the distribution of the variable will be considered statistically significant different between treatment groups if the p-value is <0.0005.

8.1. SUBJECT DEMOGRAPHICS

Subject demographics are country, age (years), gender, weight [kg], height [m], body mass index (BMI) [kg/m²], Society of Thoracic Surgeon (STS) Predicted Risk of Mortality [%], and Logistic EuroScore II [%].

8.2. IMPLANT CHARACTERISTICS

The implant characteristics will include:

- Surgical details (including, but not limited to, Surgical Approach, Cannulation, Debridement, Universal sizer measurement, bicuspidy, and decalcification)
- Implant Concomitant Procedures
- Surgical Time (section 18.12)
 - Operating room suite (min)
 - Skin-to-skin (min)

- Extracorporeal circulation (min)
- Cross clamp (min)
- Post Implant Intraoperative Transesophageal Echocardiogram
- Cardiac Rhythm-Post Operative Evaluation
- Intraoperative Management

8.3. VALVE CHARACTERISTICS

The following variables collected in the 'Valve implant' CRF will be analyzed by means of summary statistics:

- Valve manufacturer
- Number of valves used (in cases of failure to implant)
- Valve model
 - If Perceval: Pass of Perceval sizer obturator through the annulus, Labeled valve size implanted, Removal of the guiding suture, post-dilatation using ballooning
 - If conventional valve: Valve sizing measured with manufacturer sizers, Labeled valve size implanted, Valve positioning, Suture technique, use of pledget and Cor-Knot
- Implantation Outcome
 - Implantation Outcome
 - Implantation of the randomized valve

8.4. CT SCAN

The characteristics of native valves measured preoperatively by CT scan are: LVOT diameter, Aortic Annulus mean diameter, Annulus perimeter, Annulus surface, Sinus of Valsalva diameter, Sino tubular junction (STJ) diameter, Ascending aorta, and Ratio STJ/annulus.

8.5. MEDICAL HISTORY

Medical history and patient risk factors will include Coronary Artery Disease, Angina, Myocardial Infarction, Heart Failure, Carotid Artery disease, Previous Carotid Artery Surgery or Percutaneous Transluminal Carotid Angioplasty (PTCA), Stroke, Transient Ischemic Attack (TIA), Endocarditis, Peripheral Vascular Disease, Pulmonary Hypertension, Chronic Lung Disease, Diabetes, and Dyslipidemia/pecify.

8.6. OTHER BASELINE CHARACTERISTICS

For parameters collected on more than 1 occasion during the study including baseline, the assessment at baseline will be presented with assessments collected later on in the study and not in a separate table. These parameters are:

- NYHA class
- Signs of Infections
- Modified Rankin Scale
- NIHSS Score
- Vital signs
- Electrocardiogram (ECG)
- Site Reported Echocardiographic Values:
 - Aortic Mean Pressure Gradient (MPG), Aortic Peak Pressure Gradient (PPG), Sub aortic gradient, Left Ventricular Ejection Fraction (LVEF), Effective Orifice Area (EOA), Effective orifice area indexed (EOAi), Aortic Peak Velocity (VmaxAORTIC), LVOT Velocity max (VmaxLVOT), Doppler velocity index, LV mass, and Septum thickness.
 - Paravalvular and Central Leaks
 - MPG classification (section 18.12)
- Core-lab Reported Echocardiographic Values:
 - Aortic Mean Pressure Gradient (MPG), Aortic Peak Pressure Gradient (PPG), Mean Pressure Gradient, LVOT Peak Pressure Gradient, Mean Gradient (P2-P1), Peak Gradient 4(V2A- V2L) Left Ventricular Ejection Fraction (LVEF), Effective Orifice Area (EOA), Effective orifice area index (EOAi), Left Ventricular Mass, Left Ventricular Mass Index, Left Ventricular End Diastolic Volume, Left Ventricular End Systolic Volume, Aortic Peak Velocity (VmaxAORTIC), LVOT Velocity max (VmaxLVOT), Cardiac Output, and Cardiac Index.
 - Paravalvular and Central Leaks
- Health status (EQ-5D-5L)

For each time point, a radar chart will be created representing on the radii the mean level of each dimension.
- Blood test
 - Blood test results
 - Clinical significance of blood test values

NYHA, Echocardiographic values, Health Status, and Blood test will be analyzed to assess the trend during time. Additional details in section 11.1, 11.2, 0, and 13.2 respectively.

8.7. PRIOR AND CONCOMITANT CARDIOVASCULAR MEDICATIONS

Prior and concomitant cardiovascular medications are collected in the e-CRF as per enrollment. For the analysis, the following algorithm will be used to define prior and concomitant medication:

- Prior is all medication stopped prior to study day 1, regardless of its start date.

- Concomitant is any medication not stopped before the implant of the valve, regardless of its start date or medication started after the implant of ID.

Medication will be summarized and sorted alphabetically separately for prior and concomitant medication by Medication Type.

For each medication, the number of subjects will be displayed.

8.8. HEALTHCARE ECONOMICS

The healthcare economics data are:

- Intraoperative Management parameters (Total Number of Valve(s) Used, Cardioplegia, Bloods Units, Fluids, Inotropes, Coagulation Factor, and Hemostatic Agent), and
- Intensive Care Unit (ICU) Management data (Ventilation Time, Loss of Bleeding, Level of Lactate, Level of Creatinine during ICU, Renal replacement therapy, Use of inotropes, transfusion during ICU and details of plasma, platelet and red blood cell numbers).

9. COMPLIANCE

Compliance will be summarized to assess adherence to protocol requirements on:

- FU visits,
- NYHA class assessment,
- Site Echocardiography,
- Core Lab Echocardiography,
- ECG and
- Blood tests.

Compliance will be defined as the number of visits/assessments actually done by a subject divided by the number of visits/assessments planned for the respective period and multiplied by 100:

$$V_i \text{ Compliance [\%]} = [\# \text{ assessments at } V_i / \text{planned } \# \text{ assessments at } V_i] \times 100.$$

An assessment will be considered as performed if a complete “assessment date” is available in the corresponding CRF.

The number of planned assessments by visits are:

- 1 to 3 months FU visit:
 - Number of patients who perform 1-3 months visit/assessment +
 - Number of patients who don't perform 1-3 months visit/assessment with >90 days FU post-implant
- 1 year FU visit:
 - Number of patients who perform 1 year visit/assessment +

- Number of patients who don't perform 1 year visit/assessment with >395 (365+30) days FU post-implant
- 2 years FU visit:
 - Number of patients who perform 2 years visit/assessment +
 - Number of patients who don't perform 2 years visit/assessment with >760 (730+30) days FU post-implant
- 3 years FU visit:
 - Number of patients who perform 3 years visit/assessment +
 - Number of patients who don't perform 3 years visit/assessment with >1125 (1096+30) days FU post-implant
- 4 years FU visit:
 - Number of patients who perform 4 years visit/assessment +
 - Number of patients who don't perform 4 years visit/assessment with >1491 (1461+30) days FU post-implant
- 5 years FU visit:
 - Number of patients who perform 5 years visit/assessment +
 - Number of patients who don't perform 5 years visit/assessment with >1856 (1826+30) days FU post-implant

At each time point, patients who complete the visit/assessment will be classified as "Completed inside window" according to the following rules:

- 1 to 3 months FU visit: if visit/assessment is performed within 30-90 days after the day of the surgery
- 1 year FU visit: if visit/assessment is performed at 365 ± 30 days after the day of the surgery
- 2 years FU visit: if visit/assessment is performed at 730 ± 30 days after the day of the surgery
- 3 years FU visit: if visit/assessment is performed at 1095 ± 30 days after the day of the surgery
- 4 years FU visit: if visit/assessment is performed at 1460 ± 30 days after the day of the surgery
- 5 years FU visit: if visit/assessment is performed at 1825 ± 30 days after the day of the surgery

Patients who complete the visit/assessment not classified as "Completed inside window" will be classified as "Completed outside window".

10. PRIMARY ANALYSIS

10.1. PRIMARY ENDPOINT

The primary endpoint to assess the safety and efficacy of Perceval valve versus standard sutured stented valves is the freedom from MACCE (composite endpoint of all cause death, myocardial infarction, stroke, and valve re-intervention) at one year based on CEC adjudication.

10.2. TESTING STRATEGY AND MULTIPLICITY ADJUSTMENT

The primary analysis will compare Perceval valve (Treatment arm) vs. standard sutured stented valve (Control arm) on the Per Protocol population.

A one-sided non-inferiority test, using the non-inferiority margin $\Delta=0.05$, will be performed to compare the two arms on the proportion of subjects that are event-free at one year (primary analysis). The null hypothesis is that the Perceval arm is inferior to the Control arm in the primary endpoint:

$$H_0: MACCE_{CONTROL} - MACCE_{PERCEVAL} \geq \Delta$$

$$H_1: MACCE_{CONTROL} - MACCE_{PERCEVAL} < \Delta$$

where $MACCE_j$ is the one-year event-free rate for arm j.

Superiority will be tested if non-inferiority is met. In this case, the null hypothesis is that the Perceval arm is not superior to the Control arm in the primary endpoint:

$$H_0: MACCE_{PERCEVAL} \leq MACCE_{CONTROL}$$

$$H_1: MACCE_{PERCEVAL} > MACCE_{CONTROL}$$

where $MACCE_j$ is the one-year event-free rate for arm j.

This superiority test is nested hierarchically within the non-inferiority comparison and is a closed-testing procedure, thus no alpha adjustment is required.

10.3. PRIMARY ANALYSIS

The primary analysis will calculate the Bayesian posterior probability that the difference [$MACCE_{CONTROL} - MACCE_{PERCEVAL}$] is lower than 0.05 (predetermined non-inferiority margin):

$$\Pr(MACCE_{CONTROL} - MACCE_{PERCEVAL} < 0.05 \mid \text{Data})$$

The null hypothesis will be rejected, and non-inferiority concluded, if the posterior probability exceeds 0.9775 at the final analysis. This threshold was selected based on simulations to control the Type I error rate at 2.5% one-sided (CIP Appendix 8).

The probability $\Pr(MACCE_{CONTROL} - MACCE_{PERCEVAL} < 0.05 \mid \text{Data})$ is calculated on the basis of simulation after the definition of the posterior distribution of p_j according to the following steps:

1. The number of responders X_j is modeled in arm j as $X_j \sim \text{Binomial}(n_j, p_j)$ where n_j is the number of subjects for arm j and p_j is the proportion of subjects that are event-free at one year (response rate);
2. The response rates p_j are then transformed and modeled independently on the log-odds scale. They have a Normal prior distribution:

$$[\theta_j] = \left[\log \left(\frac{p_j}{1 - p_j} \right) \right] \sim N(\theta_0, \sigma_0^2)$$

with $\theta_0 = 1.99$ and $\sigma_0^2 = 3^2$ so that when converted back to the probability scale, this prior is centered at 0.88 (the expected event-free rate for the control arm);

3. One million (1000000) posterior samples for p_j in each arm will be drawn using a standard Markov chain Monte Carlo (MCMC) technique (random walk Metropolis-Hastings algorithm) after discarding the initial set of burnin samples. The calculation of the probability $\Pr(\text{MACCE}_{\text{CONTROL}} - \text{MACCE}_{\text{PERCEVAL}} < 0.05 \mid \text{Data})$ will be done as

$$\frac{\#\text{times} [\text{MACCE}_{\text{CONTROL}} - \text{MACCE}_{\text{PERCEVAL}} < 0.05]}{1000000}$$

In case of test for superiority, the Bayesian posterior probability of superiority

$$\Pr(\text{MACCE}_{\text{CONTROL}} < \text{MACCE}_{\text{PERCEVAL}} \mid \text{Data})$$

will be assessed in the Per Protocol population and will be provided. Superiority will be claimed if the above probability exceeds 0.9775. In order to calculate the probability of superiority, one million (1000000) simulations will be run using the posterior distribution on p_j in each arm, and the calculation of the probability $\Pr(\text{MACCE}_{\text{CONTROL}} < \text{MACCE}_{\text{PERCEVAL}} \mid \text{Data})$ will be done as

$$\frac{\#\text{times} [\text{MACCE}_{\text{CONTROL}} < \text{MACCE}_{\text{PERCEVAL}}]}{1000000}$$

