8 DESIGN OF THE CLINICAL INVESTIGATION

8.1 TRIAL TYPE

This is a prospective, randomized, stratified non blinded multi-center, international, post market trial assessed in a non-inferiority study.

The trial has a flexible sample size that will be determined adaptively. The trial will enroll up to 1234 subjects, but accrual may stop earlier at approximately 900 or 1050 subjects (see section 10.2). These subjects will be enrolled at approximately 60 worldwide investigational sites where the device is commercially available. Regardless of the sample size selected, follow up of subjects will continue annually up to 5 years. The primary endpoint will be reached at 1 year FU and, consequently, the planned primary analysis will be performed 12 months following the end of accrual.

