Superiority will be tested if non-inferiority is met. This superiority test is nested hierarchically within the non-inferiority comparison and is a closed-testing procedure, thus no alpha adjustment is required. The Bayesian posterior probability of superiority $\Pr(\text{MACCE}_{\text{CONTROL}} < \text{MACCE}_{\text{PERCEVAL}} \mid \text{Data})$ will be assessed in the Per Protocol population will be provided. Superiority will be claimed if:

$$\Pr(\text{MACCE}_{\text{CONTROL}} < \text{MACCE}_{\text{PERCEVAL}} \mid \text{Data}) > 0.9775.$$

Non-inferiority will be assessed in the Per Protocol population as primary analyses [23, 24]. Sensitivity analyses on the primary endpoints will be performed using different assumptions and populations (section 10.1.4)

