10.4.2 MODIFIED ITT

The “modified Intention-To-Treat Population” (mITT) will include all randomized subjects (corresponding to the ITT population) who receive a study valve (Perceval or standard sutured stented valve). All the efficacy analyses will be performed on this population as key sensitivity analysis. Subjects will be allocated to treatment group based on the treatment to which they were randomized (“as randomized” principle).

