16.1 PROTOCOL DEVIATIONS

Investigators of the trial are not allowed to deviate from the protocol requirements. In particular, it is recommended to make every effort to avoid introduction of biases caused by protocol deviations. If a deviation should occur it shall be listed and reported in the appropriate eCRF.

The Sponsor will assess the seriousness of the deviation classifying these as major or minor; and will present the list of the deviations to the Steering Committee (SC). The final decision about the seriousness will be taken by the SC.

Major deviations are defined as changes in the conduct of the trial different from what is specified in the protocol that may potentially compromise the subject's rights, safety, and well-being, or the completeness, accuracy, reliability, or scientific integrity of the trial data. Accrual of major deviations by a site may lead to no further participation within the study as reported in section 18.3.

Major and minor deviations will be validated before data lock and prior to the statistical analysis being performed.

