6.5. PER-PROTOCOL POPULATION

The “Per-Protocol” population (PP) is defined as all randomized and implanted patients attending the scheduled follow-up visits up to 1 year at minimum and without the following major protocol deviations:

- Assessment/Procedure (related to primary endpoint) Incomplete/Not Done
- Serious Adverse Event Not Reported
- No adherence to randomization allocation
- No consent obtained or if consent obtained after implant.

Further major protocol deviation may be detected by the Steering Committee and appropriately reported in the eCRF. In the exceptional event that “other” reasons requiring exclusion from the PP become apparent during the final data review, these will be suitably documented at that time in the final data review report (which will be prior to database lock).

Primary efficacy analysis will be performed on this population. The PP population will be used for analyses of primary and secondary endpoints.

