10.4. SENSITIVITY ANALYSES

The primary analysis will be assessed in sensitivity analyses using different assumptions and populations:

- the primary analysis will be repeated on the mITT population. For this analysis, missing data for the primary endpoint will be imputed using the same procedure used for the interim analysis (see Section 15). This analysis will be performed to assess the robustness of the results to protocol deviations: mITT analysis provides a “real life” scenario, in which participants may not comply to the protocol.
- the proportion of subjects that are event-free at one year will be estimated by means of a logistic regression model including as covariates the implanted valve groups (Perceval or standard sutured stented valves) and the stratification factors:

- country, and
- surgical approach.

This method allows to assess the sensitivity of non-inferiority results to possible confounding impact of the stratification factors.

A 97.5% one-sided upper confidence limit will be computed from the logistic model for the difference ($MACCE_{CONTROL} - MACCE_{PERCEVAL}$). The non-inferiority of Perceval to the Control will be confirmed if the upper confidence limit is lower than 0.05 (Δ). This sensitivity analysis of non-inferiority will be assessed in the Per Protocol Population.

- the one-year freedom from MACCE will be evaluated using the Kaplan-Meier estimates for cumulative freedom from MACCE and the Greenwood standard errors for each arm (as planned in the CIP before amendment). A 97.5% one-sided upper confidence limit will be computed for the difference ($MACCE_{CONTROL} - MACCE_{PERCEVAL}$) where $MACCE_j$ is the survival estimated by the Kaplan-Meier algorithm for arm j. The Perceval arm will be confirmed not inferior to the Control if the upper confidence limit is lower than 0.05 (Δ).

The test statistic is

$$\frac{MACCE_{PERCEVAL} - MACCE_{CONTROL} + \Delta}{\sqrt{VAR(MACCE_{PERCEVAL}) + VAR(MACCE_{CONTROL})}}$$

where VAR()s are the variances estimated by Greenwood's formula. The null hypothesis will be rejected if the test statistic is greater than 1.96. This sensitivity analysis of non-inferiority will be assessed both in PP and mITT populations in order to confirm the robustness of results to statistical method and protocol deviations.

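### Superiority on one-year freedom from MACCE is claimed from the Per-Protocol set, with no requirement that the as-randomised mITT analysis agree

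*SAP*

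**What the plan says.** Protocol 10.1.1 and SAP 10.2 test superiority once non-inferiority has been met and regard the nested order as making any alpha adjustment unnecessary. Both documents fix the analysis set. In Protocol 10.1.1 the superiority probability "will be assessed in the Per Protocol population will be provided. Superiority will be claimed if" it is above 0.9775. In SAP 10.3 it "will be assessed in the Per Protocol population and will be provided. Superiority will be claimed if the above probability exceeds 0.9775". The only precondition is non-inferiority, which is also judged in PP. References 23 and 24 are cited in Protocol 10.1.1 for PP as the primary set for non-inferiority. No reason is given for using PP for superiority.

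The mITT set (randomised, received a study valve, analysed as randomised) has a supporting role. Protocol 10.4.2 says "All the efficacy analyses will be performed on this population as key sensitivity analysis". SAP 10.4 says "the primary analysis will be repeated on the mITT population", with missing outcomes imputed as in SAP 15, and SAP Table 4 marks the primary endpoint for both sets. The explicit confirmation rules in Protocol 10.1.4 and SAP 10.4 (upper limit below 0.05, statistic above 1.96) concern non-inferiority. Neither document says what follows if PP and mITT disagree on superiority.

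**The concern.** Protocol 8.1 describes the design: "This is a prospective, randomized, stratified non blinded multi-center, international, post market trial assessed in a non-inferiority study". Under SAP 6.5, patients leave PP for endpoint-related procedures not done, unreported serious adverse events, non-adherence to allocation, or consent missing or obtained after implant. In addition, "Further major protocol deviation may be detected by the Steering Committee and appropriately reported in the eCRF". Protocol 16.1 adds that "The final decision about the seriousness will be taken by the SC". Some of these criteria can be related to outcome, and the relation can differ between arms when treatment is known.

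If that happens, the PP comparison is no longer the randomised one, and the false-superiority rate moves away from the nominal 1 − 0.9775 = 2.25%. Closed testing deals with multiplicity. It does nothing about selection. At stake is a superiority claim on the trial's primary endpoint that would comply fully with the plan while the as-randomised data did not support it.

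**Working it through.** **Reproducing the plan's own figures.** The documents give operating characteristics for non-inferiority only. With 10% attrition, 1234 × 0.9 / 2 ≈ 555 PP patients per arm, and z(0.9775) = 2.005. At 91% event-free in both arms, SE = √(2 × 0.91 × 0.09 / 555) = 0.01718 and power = Φ(0.05/0.01718 − 2.005) = 0.817, against 0.805 stated. At 88% the result is 0.712, against 0.704. These are fixed-sample approximations to an adaptive design and are close enough. Exact enumeration with the plan's N(1.99, 3²) log-odds prior and the superiority rule at no true difference gives 2.25% (88%) and 2.31% (91%) at 555 per arm. The threshold is therefore sound when selection is unrelated to outcome. The weakness lies in the analysis set.

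**Illustrating selection.** From the documents: 617 per arm (maximum sample size), 9% MACCE (1 − 0.91), threshold 0.9775. Assumed: a fraction f excluded from PP in each arm, excluded controls at 9%, excluded Perceval patients at rate e, and no true difference. The 10% in Protocol 10.3 is attrition from enrolment to PP, not the gap between PP and mITT, so f is shown at 5% and 10%.

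- PP Perceval event rate: p = (0.09 − f·e)/(1 − f); control c = 0.09; n = 617(1 − f)
- P(claim) = 1 − Φ(2.005 − (c − p)/SE), with SE = √{[p(1 − p) + c(1 − c)]/n}

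Example, f = 10%, e = 25%: p = (0.09 − 0.025)/0.9 = 0.0722; n = 555.3; SE = 0.01638; (c − p)/SE = 0.01778/0.01638 = 1.086; P(claim) = 1 − Φ(0.919) = 17.9%.

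| False superiority | e = 9% | e = 15% | e = 20% | e = 25% |
|---|---|---|---|---|
| PP, f = 5% | 2.25% | 3.5% | 4.9% | 6.8% |
| PP, f = 10% | 2.25% | 5.4% | 10.2% | 17.9% |
| Half of excluded outcomes unknown, mITT, f = 5% | 2.25% | 2.8% | 3.3% | 4.0% |
| Half of excluded outcomes unknown, mITT, f = 10% | 2.25% | 3.5% | 4.9% | 6.8% |

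The mITT rows replace f by f/2, because unknown outcomes imputed from the same arm leave the bias in place for those patients. If every excluded outcome is known, mITT returns to 2.25%; if none is, there is no gain over PP. Exact enumeration with the plan's prior agrees with the PP rows (3.6/5.1/7.0% and 5.5/10.4/18.2%). Reversing the asymmetry lowers the PP rate to between 1.4% and 0.6% (f = 5%) and between 0.8% and 0.1% (f = 10%).

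**How often the two sets disagree.** In 2,000,000 simulated trials per case (31 or 62 excluded per arm, all outcomes known), PP claims superiority and mITT does not in 1.5%, 2.8% and 4.7% of trials (f = 5%) and in 3.3%, 8.0% and 15.7% (f = 10%) for e = 15%, 20% and 25%. Without differential selection the figures are 0.5% and 0.7%. The mITT false-superiority rate was 2.2% to 2.3% throughout.

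**A different mechanism.** Take 10% random loss to PP and let an extra 10%, 20% or 30% of Perceval-arm MACCE patients drop out of PP. PP-only false superiority is then 6.5%, 15.8% and 32.9%, while mITT alone stays at 2.2% to 2.3%.

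**A borderline case under the plan's prior.** PP events of 35/586 (Perceval) and 53/586 (control) give a posterior probability of 0.9776, a claim. Adding 31 excluded patients per arm, with 4 Perceval and 3 control events, gives 39/617 and 56/617 and a probability of 0.966, no claim.

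**The case against.** The strongest objection is one of consistency. The same formula with true MACCE of 14% against 9%, and excluded Perceval patients 6, 11 or 16 points above their arm, puts PP false non-inferiority at 3.3%, 4.6% and 6.1% (f = 5%) or 4.9%, 8.9% and 14.9% (f = 10%). That is similar inflation, and the mITT analyses do not bind the non-inferiority conclusion either. The difference is that PP is the argued and referenced choice for non-inferiority, and SAP 10.4 adds an explicit mITT confirmation criterion there. For superiority there is neither.

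Several safeguards count in the plan's favour. SAP 2.4 treats a patient as adherent if the allocated valve was attempted, even if the other arm's valve was then implanted, which would keep failed implants in PP. SAP Table 8, however, ties adherence to the randomised valve being implanted at first attempt. Table 8 also omits the visit attendance that SAP 6.5 requires, so PP may lose fewer patients than SAP 6.5 implies. Deviations are validated before data lock, and every effort is made to blind the events committee. These measures narrow the room for selection but do not remove it in an open trial.

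The sizes rest on assumed inputs. If exclusions carry equal risk in both arms, the rate stays at 2.25%. That is conceded.

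mITT has limits of its own. It omits randomised patients who received no study valve, so it is not full ITT, and imputation does not cure informative missingness. Moving the claim to mITT also allows a claim that PP does not support, in about 0.5% to 0.7% of null trials without differential selection and 1.0% to 2.1% under the reverse asymmetry. Those claims fall within an mITT error rate that holds at its nominal level when outcomes are known.

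**Conclusion.** The concern holds. Both documents let superiority be claimed from PP alone, and no passage makes the claim depend on the as-randomised result. A reader would probably see a disagreement, because the mITT repeat is planned and can be read to include the superiority probability, but the stated rule would still let the claim stand.

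The possible error ranges from no change (2.25%) to 3.5% to 6.8% with 5% excluded and 5.4% to 17.9% with 10% excluded, under the assumed asymmetry against excluded Perceval patients; it falls below nominal under the opposite asymmetry. These figures assume the fixed maximum sample size, without the interim looks. Confidence is high about what the text permits. The actual bias in this trial cannot be known from the documents. The primary non-inferiority conclusion is outside the proposed change.

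**What to change.** Keep PP as the primary set for non-inferiority. Once that is met, claim superiority only if Pr(MACCE_CONTROL < MACCE_PERCEVAL | Data) exceeds 0.9775 in the mITT population as randomised, using the SAP 10.4 repeat with SAP 15 imputation. Report the PP superiority probability as supportive. State in SAP 10.4 that the mITT repeat includes the superiority probability, since the present wording only implies it.

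The rule must change in both Protocol 10.1.1 and SAP 10.3. Protocol 10.6 requires either an amendment or an entry with rationale in the SAP section on changes from the protocol; SAP 3.1 currently records none. Make the change before the lock for the primary analysis.

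No new data are needed, and the mITT run is already planned. The price is possible dilution of a true superiority effect, and residual bias where outcomes are missing for reasons related to the endpoint.
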